**FORM: Application for Human Research**

NUMBER	FORM DATE	PAGE
F200	02/2014	29 of 39

specific functional and structural changes. Such information will identify target regions that are most affected by MBLT.

4) "If SPLT is better than MBLT"—it would be unexpected to find the placebo group outperforming the MBLT group. However, such a finding would argue against melatonin suppression as the likely candidate for improvement. Such an intriguing finding would necessitate follow on research to identify the causal factors, and if replicated, could in itself lead to new discovery of an alternative treatment approach. Again, secondary correlational analyses with imaging and neurocognitive measures and analysis of the direction of the effects will guide such interpretations.

Per the Department of Defense, all study data will be deposited on the Federal Interagency Traumatic Brain Injury Research Informatics System (FITBIR) database. This is a protected database that provides training approximately monthly.

The National Institutes of Health (NIH), in partnership with the Department of Defense (DoD), is building a secure, centralized informatics system (database) for TBI research. It will serve as a central repository for new data, link to current databases and allow valid comparison of results across studies. The database builds upon an effort to create common data elements for the study of TBI - which are essentially definitions and guidelines about the kinds of data that should be collected, and how to collect these data in clinical studies.

The Federal Interagency Traumatic Brain Injury Research (FITBIR) informatics system is a collaborative effort involving the NIH Institutes and Centers (ICs) and the US Army Medical Research and Material Command (USAMRMC) to develop a biomedical informatics system and data repository for Traumatic Brain Injury (TBI) research.

The FITBIR Informatics System is an extensible, scalable informatics platform for TBI relevant data (medical imaging, clinical assessment, environmental and behavioral history, etc.) and for all data types (text, numeric, image, time series, etc.). FITBIR was developed to share data across the entire TBI research field and to facilitate collaboration between laboratories, as well as interconnectivity with other informatics platforms.

Data submitted to the FITBIR Informatics System will be de-identified such that the identities of data subjects cannot be readily ascertained or otherwise associated with the data by the FITBIR staff or secondary data users. In addition, de-identified data will be coded using a unique code known as a Global Unique Identifier (GUID). Use of the GUID minimizes risks to study participants because it keeps one individual's information separate from that of another person without using names, addresses, or other identifying information. The unique code also allows FITBIR to link together all submitted information on a single participant, giving researchers access to information that may have been collected elsewhere. The GUID is a computer-generated alphanumeric code [example: 1A462BS] that is unique to each research participant (i.e., each person's information in FITBIR—or each subject's record—has a different GUID). FITBIR will assist investigators in how to create the GUID, which is an essential requirement for uploading data to FITBIR.

**FORM: Application for Human Research**

NUMBER	FORM DATE	PAGE
F200	02/2014	30 of 39

## 8) Risks to subjects

The psychological, social, economic and legal risks of the assessment, light exposure, and MRI acquisition components of this study are minimal, and no physical or economic harm is anticipated. The questionnaires and brief clinical interview may ask questions that produce discomfort in some participants, but this is not expected. The instruments used here are all published and have been used with large numbers of human participants without ill effect.

The Philips goLITE device is a commercially available product that has no significant known harmful effects. The device has been used for treatment of SAD and jet lag and has undergone extensive safety testing based on U.S. and international standards for photobiological safety of light devices. As shown in the appendix to this protocol, an independent optical safety analysis was provided to the manufacturer of the devices on 30 August 2009. The analysis indicated that the averaged radiance of the array of LEDs is below hazardous standards set by the Illuminating Engineering Society of North America (IESNA) and the International Commission on Illumination, and International Electrotechnical Commission, and meets criteria for an Exempt product without photobiological risk when used as indicated. During normal use of the device, as will be standard procedure in the present study, participants will only view the LED array at an indirect angle (i.e., the subject will be instructed NOT to look directly at the LEDs but to keep them visible in the periphery). When the LED panel is viewed off axis, at an indirect angle as directed, the LED radiances fall below internationally recognized levels for indefinite viewing. Thus, when viewed as directed, the goLite device can be safely viewed at maximum intensity for as long as desired (although participants will be instructed to use it for no longer than 30 minutes each day).

Although normal usage of the device has no known hazards, the primary and most extreme health concern, which is an issue with any form of blue wavelength light exposure, is photoretinitis, or “blue-light hazard”, which may occur when exposure surpasses internationally recognized limits ( $10\text{mWcm}^2\text{sr}^{-1}$ ). Photoretinitis involves photochemical damage to the retina as a result of prolonged exposure to extremely bright light (e.g., excessive sun exposure; snow blindness) and can have symptoms that are minor and dissipate quickly (e.g., afterimages), or less commonly, long-term degradation of vision. The risk of photoretinitis is influenced by the wavelength, brightness, and duration of light exposure. According to the ocular safety analysis and safety information provided by the manufacturer, the goLITE BLU produces only 8.9% of the long-term exposure limit, and therefore there is no specified limit to viewing, even for direct fixation. When used as directed, as will be the standard procedure in the present study, the goLITE has been shown to be safe even at a factor of 100 times the normal usage recommendations. The safety analysis, which was reportedly reviewed and concurred with by the FDA, suggests that the exposure to hazardous light from the goLITE falls below all internationally recognized standards and meets criteria for a non-risk, exempt category device. According to the ocular safety analysis, even the most extreme example of staring directly at a single unshielded diode would require 27.8 minutes of direct fixation before long term fixation exposure limits could be reached. However, this eventuality is extremely unlikely for the following reasons:

- 1) The high luminance of the diodes would be discomforting to stare at for more than a brief time. Humans find direct staring directly at bright light sources aversive, and the discomfort would

**FORM: Application for Human Research**

NUMBER	FORM DATE	PAGE
F200	02/2014	31 of 39

likely preclude an individual from voluntarily gazing directly at a single diode for more than a few moments.

- 2) Participants will be informed about the potential for visual discomfort and possible hazards of long term direct staring at the diodes. This information will be listed prominently in the informed consent document and will be described orally to the participant as well.
- 3) Participants will be given a hands-on demonstration about how to use the device. During the interactive demonstration, the participant will practice the correct method for viewing and will be warned about not staring for prolonged periods at the diodes.
- 4) Participants will be given written instructions with a visual diagram outlining normal safe positioning and use of the device.

5) A warning label will also be printed and taped to the face of each device which states  
“WARNING: DO NOT STARE DIRECTLY AT THE LED SCREEN”

Participants will be instructed on proper use of the device and the importance of not looking directly at the LEDs for extended periods. Of course, individuals differ in their sensitivity to light and it is possible that unanticipated eye fatigue or irritation could occur. Direct staring at the diodes could lead to the presence of temporary afterimages. Participants will be instructed to discontinue use and contact the principal investigator immediately if any unusual sensations or discomforts are noticed.

The MR imaging procedure does not pose a significant risk to subjects meeting the entry criteria for this study. There is no known hazard associated with MR imaging. Nuclear magnetic resonance imaging does not involve ionizing radiation such as that associated with X-ray or radionuclide techniques. All studies will use radiofrequency power deposition and gradient switching which have been approved by the FDA. We do not know if MRI scanning presents a risk to unborn fetuses, so we will ask all females of childbearing potential to complete a urine pregnancy test immediately prior to the scan. This pregnancy test will be performed in the Department of Psychiatry.

Although MR imaging is thought to be hazard free, some subjects may experience discomfort. Noise from the MRI machine can cause discomfort. Even though most subjects tolerate the scanning session, some subjects may find the enclosed space of the MRI device to be physically uncomfortable or anxiety producing. Some subjects may experience tingling in the extremities or numbness caused from remaining in the same position for a long duration. Measures will be taken to minimize these discomforts.

Risks and discomforts during PSG are generally minimal. On rare occasions some mild skin irritation or rash may emerge while wearing the electrodes, but this normally resolves upon removal of the electrodes. Participants will wear the electrodes for less than an hour, so such irritation is highly unlikely in such a short time.

- 6) There is the risk of some skin irritation from the EEG/EKG leads being attached to the skin. This can be alleviated by application of lotion/cream.
- 7) There are no anticipated risks associated with saliva collection. These samples will be collected via a small plastic tube placed in the lower part of your mouth. These samples will be labeled with a unique study ID number only and will be kept in the research suite only accessible to authorized study personnel.
- 8) Subjects will see images they may find distressing during one task while in the scanner.

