## **12) Subject compensation**

### **Main Study Arm:**

Subjects will receive \$1000 for completion of both study sessions and successful adherence to the daily light exposure treatment. This payment is also intended to cover all transportation expenses to and from the hospital.

If subjects choose to withdraw from the study prematurely, they will be compensated at a rate of \$25/hour for the time they were undergoing scanning and testing, according to the following schedule:

**FORM:** Application for Human Research

NUMBER	FORM DATE	PAGE
F200	02/2014	34 of 39

- Discontinuation during or following the initial visit, subjects will be paid \$50 for completing the initial clinical assessment and questionnaires.
- Discontinuation before the end of second visit (i.e., first testing and scanning session): \$25/hour, up to a maximum of \$250 total, following return of all study-related equipment.
- Discontinuation any time during the 6-week light exposure period: \$275 maximum total payment, following return of all study-related equipment.
- Discontinuation during but before the end of the third visit: \$275 plus \$25/hour during the third visit, up to a maximum total payment of \$475, following return of all study-related equipment.
- Completion of study procedures up to the end of the third visit and return of all study equipment: \$900.
- Completion of all study procedures up to the end of the third visit, return of all study equipment, and evidence that all at-home study procedures were followed (i.e., regular compliance with the use of wrist activity monitors, sleep diaries, and light exposure device): \$1,000. If subjects fail to return the Actiwatch and/or Light Device, subjects will receive no compensation.

If subjects choose to participate in the 6-week follow-up period after the initial 7 weeks:

- Discontinuation at any time during the 6-week period post light therapy: \$1,000 plus \$33.33/week for each week of participation after the end of the third visit.
- Completion of all study procedures for the entire duration of the study (13 weeks), including return of all study equipment within 10 days and evidence that all at-home procedures were followed (i.e., regular compliance with the use of wrist activity monitors and sleep diaries): \$1,200.

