## **15) Withdrawal of subjects**

If significant psychopathology or other disqualifying condition is discovered during the psychiatric assessment or if it becomes evident that the participant is unable or unwilling to comply with study procedures, research study staff may withdraw that individual from the study.

Subjects can voluntarily withdraw from the study at any time by speaking with the PI or study team. The study will then ensure the subject withdraws from the study safely and will provide any necessary follow-up care.

In order to protect subjects, study resources and the integrity of study data, the Principal Investigator reserves the right to remove any subject at his discretion from the study. This will be communicated to prospective subjects during the consent process.

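### A participant who stops the lamp as the safety text instructs may lose payment, and possibly their place in follow-up, because no section exempts such a stop

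*Combined protocol and SAP*

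**What the plan says.** Four parts of Section 3 of the combined document bear on this point.

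- **Item 8, Risks to subjects.** After naming eye fatigue, irritation and temporary afterimages as possible, the text says: "Participants will be instructed to discontinue use and contact the principal investigator immediately if any unusual sensations or discomforts are noticed". The instruction is the same for both arms. It does not mention restarting, later visits or pay.
- **Item 12, Subject compensation, Main Study Arm.** The headline sum, in dollars, is "1000 for completion of both study sessions and successful adherence to the daily light exposure treatment". The schedule below it requires, for this top tier, "evidence that all at-home study procedures were followed (i.e., regular compliance with the use of wrist activity monitors, sleep diaries, and light exposure device". A $900 tier covers "Completion of study procedures up to the end of the third visit and return of all study equipment". A separate line, "Discontinuation any time during the 6-week light exposure period", carries a ceiling, in dollars, of "275 maximum total payment, following return of all study-related equipment".
- **Item 15, Withdrawal of subjects.** If someone proves "unable or unwilling to comply with study procedures, research study staff may withdraw that individual from the study". Nothing distinguishes a person who stopped because item 8 told them to.
- **Item 7, Six-Week Light Exposure Treatment.** Lamp use is tracked with a power meter and the actigraph's light sensor. Staff telephone weekly about compliance and questions, and to collect an Epworth score. No question about eye symptoms or adverse events is listed for these calls.

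**The concern.** The safety instruction asks the participant to do something that two other sections can count against them. Stopping the lamp removes the evidence that the top payment requires, and the monitoring makes the stop visible. On its face, someone with sore eyes who wants full payment has a reason to keep the lamp on and say nothing.

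Two things are at stake. One is the safety record: the light-related complaints named in item 8 come to notice mainly because the participant speaks up, and the adverse-event reporting in item 14 starts only once an event is known. The other is the outcome comparison. If a symptom stop leads to withdrawal, the post-treatment assessment may be lost for a reason tied to treatment. In a trial of about 20 people per arm, each such loss is 1/20 = 5% of the arm.

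**Working it through.** The plan gives no figure of its own on this point. Its one main-arm attrition estimate (item 5, about 6 participants, 17%) pools early withdrawal with failure to comply, is not split by arm or cause, and is not used here.

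**1. The texts side by side**

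| Item | What a symptom stop triggers | Exemption for an instructed stop |
|---|---|---|
| 8 | Stop the lamp, call the investigator | Not applicable |
| 12 | Top tier needs "regular compliance with the use of wrist activity monitors, sleep diaries, and light exposure device" | None stated |
| 15 | Staff may withdraw the person | None stated |

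A participant can follow item 8 exactly and still fall short of item 12. That is a conflict in the text, not merely a missing detail.

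**2. Money at stake (inputs from item 12)**

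- Stops for most of the light period, completes the third visit: 1,000 − 900 = $100, or 100/1,000 = 10%.
- Stop classed as discontinuation in the light period: 1,000 − 275 = $725, or 725/1,000 = 72.5%, measured against the $275 ceiling.

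The first reading fits better. Item 8 concerns use of the lamp, not leaving the study, and the $900 tier differs from the $1,000 tier in not asking for evidence of home adherence. The second reading is not excluded. Item 8 speaks of discontinuing use and item 12 of discontinuation, without defining either. The lead-in about choosing to withdraw stands over the whole schedule, including the two completion tiers, so it does not separate the cases cleanly. A brief interruption may cost nothing, because item 12 asks for regular use and sets no threshold.

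**3. What silence would do to the record (illustration on assumed rates)**

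Let s be the share of blue-lamp users with eye symptoms, r the share of those who report, and n the number of users. The chance of recording no case is (1 − s × r)^n. The documents give neither s nor r. I take n = 20 from half of 40 enrolled, and n = 15 from half of the 30 complete datasets.

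| s (assumed) | n | r = 1 | r = 0.5 |
|---|---|---|---|
| 10% | 20 | 0.90^20 = 0.12 | 0.95^20 = 0.36 |
| 10% | 15 | 0.90^15 = 0.21 | 0.95^15 = 0.46 |
| 20% | 20 | 0.80^20 = 0.01 | 0.90^20 = 0.12 |
| 30% | 20 | 0.70^20 = 0.001 | 0.85^20 = 0.04 |

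This shows what follows if people stay silent. It is not evidence that they do.

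**4. Difference between arms (inputs from items 7 and 8)**

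- Irradiance, blue to amber: 1.23/0.58 = 2.12.
- Lux, blue to amber: 214/180 = 1.19.
- The blue device is put at 8.9% of the long-term exposure limit, and both safety analyses find no meaningful hazard when the devices are used as indicated.

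The two ratios differ widely, and neither converts to a symptom rate.

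**The case against.** The strongest reply is that this is silence in the text rather than a penalty. Item 8 tells people to stop the lamp, not to leave. Withdrawal under item 15 is discretionary, and near-identical wording in the Initial Assessment section concerns eligibility at the first visit. Obeying a study instruction is not plainly unwillingness to comply. No text ties pay to keeping quiet. The weekly calls also check that all is going well, the power meter and light sensor would reveal a stop without any self-report, a medical monitor is named, and item 15 promises follow-up care after voluntary withdrawal. A rule for safety stops could also sit in the consent form, payment form or lamp instructions, which are listed as attachments but are not in the text available here.

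Much of this stands. It rules out three stronger readings that a reader might infer:

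- **That harm will be under-reported.** The documents give no reporting rate, and the calls and monitoring work against silence.
- **That stopping costs $725 or ends follow-up.** The first depends on an unsettled classification and the second on staff discretion.
- **That the loss falls mainly on the blue arm.** Higher irradiance makes this conceivable, but no symptom rate is given for either arm and both devices are described as within limits.

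The conflict itself remains. The calls have no listed symptom question, follow-up care is not outcome collection, and the assurance in item 8 that withdrawal carries no penalty concerns scanner images. If an attachment already holds the rule, the application should say so.

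**Conclusion.** The point holds as a conflict between items 8, 12 and 15. A participant who follows the stop instruction for most of the light period and completes the third visit would appear to lose $100. A $725 loss is possible only if the stop is classed as discontinuation, which the text leaves open. This gives a reason not to stop or report, and it may remove people from the post-treatment assessment for a treatment-related reason.

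How often this would happen, and whether it would differ between blue and amber, cannot be determined from the documents. The probabilities in the table rest wholly on assumed symptom and reporting rates. The conclusion about missing exemptions covers the application text only. The repair is worth making because it is cheap and protects both the safety record and the randomised comparison.

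**What to change.** Reconcile items 8, 12 and 15, as follows.

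1. **Item 12 and the consent discussion.** State that lamp use stopped or interrupted after a symptom reported under item 8 does not reduce payment.
2. **Item 15.** State how such a stop relates to the wording on inability or unwillingness to comply. State also that actigraphy, diary, weekly calls and the post-treatment visit are still sought from people who stop the lamp, unless they withdraw consent or the investigator ends participation.
3. **Weekly calls (item 7).** Add a question about eye symptoms. Record the date and symptom, with arm, so that counts can be tabulated by arm. Without the question, the payment change alone could leave silent participants silent.

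Decisions about any individual's further lamp use stay with the investigator, and nothing here changes them.

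**Cost.** A few sentences in the application, one in the consent form and one question on calls already planned, with no new visit. The payment change costs $100 per affected participant on the likelier reading and $725, measured against the $275 ceiling, on the other. There is a small risk that someone claims discomfort to avoid the lamp and still be paid.

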**FORM: Application for Human Research**

NUMBER	FORM DATE	PAGE
F200	02/2014	32 of 39

Participants are informed of the disturbing images at two distinct junctures during their visit: 1) During the consenting process, the experimenter mentions that some disturbing images will be shown on a screen while the participant is in the scanner, 2) The experimenter again reminds the participant that they will be asked to view some disturbing images on a screen just prior to entering the scanner. Participants are reminded at both of these times that their participation is voluntary and that they may withdraw their participation at any time and for any reason without penalty. If the participant expresses any discomfort, the experimenter will have a brief conversation about the subject's discomfort. If any indication is given from the participant that they do not feel comfortable viewing the images, their participation will be withdrawn from the study. Participants may also push a button that they are given while in the scanner to immediately stop the study if they decide upon viewing one or more images that they do not wish to continue their participation.

